[name], Research Assistant Professor of Psychiatry and Biostatistics and Director of the Division of Quantitative Methods in the Department of Psychiatry UCCOM, has extensive expertise in the area of psychiatry and biostatistics. [name] will oversee all aspects related to database design and data management. He will lead the statistical analyses and complete exploratory post-hoc analyses. He will also assist in preparing manuscripts of the research findings.

E. Experimental Design and Methods:

Figure 1. Schedule of assessments for the 14-week trial

ASSESSMENT	SCREENING	BASELINE	WEEKS 1-11	WEEK 12 (TERMINATION)	WEEK 14 (FOLLOW-UP)
WASH-U KSADS	X	X			
Young Mania Rating Scale (YMRS)	X	X	X	X	X
Children's Depression Rating Scale-Revised (CDRS-R)	X	X	X	X	X
ADHD Rating Scale (ADHD Rating Scale-IV)	X	X	X	X	X
Clinical Global Impression-Severity (CGI-S)	X	X	X	X	X
Clinical Global Impression-Improvement (CGI-I)			X	X	X
Timeline Follow-Back	X	X	X	X	X
Child Behavior Checklist (CBCL)		X	X (Wk 4 & 8)	X	X
Teacher's Report Form (TRF)		X		X	
Children's Global Assessment Scale (CGAS)	X	X	X (Wk 4 & 8)	X	X
The Omega-3 Dietary Intake Questionnaire		X	X	X	
Columbia Suicide Severity Rating Scale (C-SSRS)	X	X	X	X	X
LIFE psychosocial functioning scales		X	X (Wk 4 & 8)	X	
Prior medical & treatment history, physical exam	X			X (physical exam)	
Vital signs	X	X	X	X	X
Urine toxicology screen & pregnancy test	X	X		X	
Serum laboratory tests (renal profile, complete blood count, liver & thyroid function tests, fasting lipid profile & glucose, and platelet function assay)	X			X	
Red blood cell omega-3 fatty acid levels	X			X	
Adverse events & adherence assessments	X	X	X	X	X
¹ H-MRS scan		X		X	
Total duration of appointment	2 hours	3 hours	1 hour	3 hours	1-2 hours

Figure 2. Study Design

DBPC=Double-blind placebo-controlled; SOC=Standard of Care Treatment

a. Methods and Procedures:

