Two-week and Long-term Follow-up: At the end of the 12 weeks patients and their legal guardians (if < 18 years) will decide whether they would like to continue (or start for those receiving placebo) omega-3 fatty acids. Regardless of the treatment chosen, all patients will return for a follow-up visit two weeks following their last visit in the DBPC study to ensure that there has been no significant worsening of their mood. Importantly, all patients will have the option to continue to participate in the BITREC, which is a longitudinal 5-year study. Since some patients will opt to continue omega-3 fatty acid treatment, this will permit us to obtain long-term effectiveness and tolerability data. Safety and efficacy assessments will be performed at all follow-up visits. Subjects will be responsible for obtaining their own omega-3 fatty acids supplementation after study completion if they wish to continue with omega-3 treatment. Omega-3 fatty acids are widely available via food, health, and supplement retail stores at a relatively low cost.

Assessments:

The Children's Depression Rating Scale-Revised (CDRS-R), a 17-item observer-rated questionnaire,^{40,41} and the

Young Mania Rating Scale (YMRS),⁴²⁻⁴⁴ an 11-item observer-rated questionnaire to assess depressive and manic symptoms, respectively. A consensus adolescent/legal guardian score for the CDRS-R and YMRS will be determined by the rater.

Subjects will also be rated using the Clinical Global Impression-Severity Scale (CGI-S), a clinician rated 7-point scale (rated from 1=normal to 7=extremely ill) to assesses overall illness severity.⁴⁵ CDRS-R, YMRS, and CGI-S will be administered at screening, baseline (concurrent with the first imaging session) and then subsequently at each weekly follow-up visit and will be used to rate symptoms during the prior week.

The CGI-Improvement Scale (CGI-I) is a clinician rated scale that assesses overall illness change

from baseline and will be administered at all post-baseline visits.

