Prediction 3: Omega-3 fatty acids will be safe and well tolerated compared with placebo. To evaluate the safety and tolerability of omega-3s we will use ANOVAs to compare change from baseline to week 12 (or endpoint) in vital signs and laboratory values. Additionally, we will determine the percentage of subjects who reported each adverse event and will examine treatment group differences in adverse events and serious adverse events using Fisher exact or χ^2 tests.

Prediction 4: Improvement in mood symptoms following treatment with omega-3 fatty acids is mediated by decreases Glu and mI levels and increases in NAA levels in the VLPFC (BA 10) and ACC (BA 24, 32). Our hypothesized model predicts that treatment produces changes in metabolite levels (Glu, mI, and NAA). These metabolite changes lead to change in mood symptoms. The mediated link between treatment and mood symptoms via metabolite levels is the *indirect treatment effect*. The *direct treatment effect* represents any residual association between treatment and mood symptoms after adjusting for the *indirect effect*. This association will be smaller in magnitude than the unadjusted association between treatment and mood symptoms (which is the *total treatment effect* or the quantity of interest in Prediction 1). For the prediction of a mediated treatment effect to be supported, two conditions must be met, i.e., significant associations between treatment and metabolite levels and between metabolite levels and mood symptoms. Prediction 4(a) is that treatment with omega-3 fatty acids will lead to decreases in Glu and mI levels and increases in NAA levels within VLPFC and ACC. It is possible for this prediction to be supported in the absence of a general association between treatment and mood symptoms (Prediction 1), which would suggest that these metabolic changes do not impact clinical outcome. Prediction 4(b) is that decreases in Glu and mI levels in VLPFC and ACC, and increases in NAA in VLPFC and ACC, will lead to decreases in

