Safety Monitoring: The data and safety monitoring plan for the proposed study will include monitoring of efficacy data by an independent Data Safety Monitoring Board (DSMB) and monitoring of tolerability data, including adverse events and serious adverse events, by the study investigators as well as the independent DSMB and the University of Cincinnati Medical Center Institutional Review Board (IRB). Adverse events will be monitored during the study using clinical interviews as well as a structured side effects questionnaire, the Side Effect Form for Children and Adolescents (SEFCA) that will be administered by an experienced clinician with extensive experience conducting clinical investigations of adolescents with mood disorders. They also will be responsible for evaluating all adverse events during study visits, which will occur at weekly visits or more frequently as necessary. Additionally, a study related physician will be accessible by pager to patients and their legal guardians 24 hours/day, 7 days/week during study participation. [name] will also be responsible for reviewing all laboratory and safety measures from all subjects following each visit. An adverse event (AE) is any unexpected medical occurrence in a patient or clinical investigation subject who is administered a product and which does not necessarily have a causal relationship with the treatment. This includes any clinical or laboratory change that occurs at any time following consent that does not typically occur in that subject and is considered clinically significant. The frequency and severity of all observed or volunteered AEs regardless of treatment group or suspected causal relationship to the study treatment will be recorded throughout the study. [name] will also be responsible for determining causal relationships between the study treatment and all AEs. Additionally, an independent, non-study related physician also will provide independent assessments of the causal relationship between AEs and the study treatment during the course of the study. Withdrawal from the study as a result of an AE or because of therapeutic measures taken to treat an AE will be at the discretion of [name]. If a subject withdraws or is withdrawn from the study for any reason, a BITREC study physician will monitor subjects with any ongoing AE until the AE is resolved or determined to be stable. All AEs (including those present during screening) will be reported. However, for analytics purposes, only post-baseline (randomization) AEs will be considered for calculating treatment group differences in AEs. A serious adverse event is any adverse experience occurring during study participation that results in any of the following outcomes: death; a life threatening adverse drug experience; inpatient hospitalization or prolongation of existing hospitalization; a persistent or significant disability/incapacity; or a congenital anomaly/birth defect. Important medical events that may not result in death, be life-threatening, or require hospitalization may be considered serious adverse experiences when, based on appropriate medical judgment of the study physician, they may jeopardize the patient or subject and may require medical or surgical intervention to prevent one of the outcomes in this definition. The judgment of whether a particular AE meets the above criteria for an SAE for the proposed study will be determined by [name], in conjunction with the proposed DSMB. It will also be [name] responsibility, to manage all SAEs and to make referrals for

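### The between-arm adverse event comparison has no stated end point, so week 12–14 events under self-chosen omega-3 use could be counted by randomized arm

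*Combined protocol and SAP*

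**What the plan says.** The relevant text is spread over four places in the combined protocol and SAP.

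- **Section E.b, Safety Monitoring.** All events are to be reported, including those seen during screening, but "only post-baseline (randomization) AEs will be considered for calculating treatment group differences in AEs". Events "regardless of treatment group or suspected causal relationship to the study treatment will be recorded throughout the study".
- **Section E.b, Data Analyses, Prediction 3.** ANOVAs will "compare change from baseline to week 12 (or endpoint) in vital signs and laboratory values". The next sentence turns to adverse events: "we will determine the percentage of subjects who reported each adverse event and will examine treatment group differences in adverse events". It covers SAEs in the same way, names Fisher's exact test or a chi-square test for both, and gives no time window.
- **Section E, Figure 1.** The figure is titled "Schedule of assessments for the 14-week trial". The row "Adverse events & adherence assessments" is marked at every visit, including the week 14 follow-up.
- **Section E.a, Two-week and Long-term Follow-up.** At the end of the 12 weeks patients and guardians "will decide whether they would like to continue (or start for those receiving placebo) omega-3 fatty acids". Whatever they choose, all patients return two weeks later, and safety is assessed at every follow-up visit.

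Nothing in the documents removes week 12–14 events from the arm comparison or classifies them by the supplement actually taken.

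**The concern.** Prediction 3 is that omega-3 is safe and well tolerated relative to placebo. Under the rule as written, a placebo patient who starts omega-3 at week 12 and reports an omega-3 effect at week 14 (the fishy burp named under Risks/Discomforts is the obvious case) would be a placebo-arm case. That raises the placebo rate and moves the comparison towards no difference, which is the result that favours the prediction. The events most exposed are those most likely to be caused by the supplement.

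Blinding is a second issue. Offering some patients the choice to continue, and those on placebo the choice to start, suggests that assignment is known by then, although the protocol does not say so. Anyone who takes up omega-3 openly knows what they are taking. Reports from these two weeks are therefore probably not blinded, and they do not belong in a double-blind contrast.

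**Working it through.** **What can be checked.** The plan states no adverse event rate, crossover share, or power or significance level for this comparison, so it has no figure to reproduce. The calculations below only show how large the effect could be.

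**Inputs**
- From the documents: 30 patients per arm; Fisher's exact test as one of the two named tests; an optional start of omega-3 at the end of week 12; a further event assessment two weeks later.
- Assumed: 12-week event risk of 40% on omega-3 and 10% on placebo; two-sided α = 0.05 (the plan states 0.05 only for its exploratory analyses); half of placebo patients starting omega-3 at week 12.

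**Window closed at week 12.** The difference is 40 − 10 = 30 points and the risk ratio is 4.0. Fisher power by full enumeration at 30 per arm is 70.5%.

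**Window open to week 14, constant weekly hazard**
- Hazard on omega-3: −ln(0.60)/12 = 0.0426 per week. Two-week risk: 1 − exp(−2 × 0.0426) = 8.2%.
- Hazard off omega-3: −ln(0.90)/12 = 0.0088 per week. Two-week risk: 1.7%.
- Chance of no new event in two weeks when half take omega-3: 0.5 × 0.9184 + 0.5 × 0.9826 = 0.9505.
- Placebo arm to week 14: 1 − 0.90 × 0.9505 = 14.5%.
- Omega-3 arm, half continuing: 1 − 0.60 × 0.9505 = 43.0%.
- Omega-3 arm, all continuing: 1 − 0.60 × 0.9184 = 44.9%.

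**Window open to week 14, onset clustered after starting**
- Placebo rate = p0 + (1 − p0) × f × q, where f is the share starting and q the chance that a starter reports the event within two weeks. New events in the omega-3 arm are ignored.
- With p0 = 0.10, f = 0.50 and q = 0.30: 0.10 + 0.90 × 0.50 × 0.30 = 23.5%. The difference is 40 − 23.5 = 16.5 points.
- Over f = 25–75% and q = 20–40%, the placebo rate runs from 14.5% to 37%, the difference from 25.5 to 3 points, and Fisher power from 51% to 3%.

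| Scenario (half of placebo patients start) | Omega-3 | Placebo | Difference | Risk ratio | Fisher power |
|---|---|---|---|---|---|
| Closed at week 12 | 40.0% | 10.0% | 30.0 | 4.0 | 71% |
| Constant hazard, all of omega-3 arm continue | 44.9% | 14.5% | 30.4 | 3.1 | 66% |
| Constant hazard, half of omega-3 arm continue | 43.0% | 14.5% | 28.5 | 3.0 | 61% |
| Early-clustered onset, q = 30% | 40.0% | 23.5% | 16.5 | 1.7 | 20% |

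Within either onset pattern, the more placebo patients start, the smaller the contrast. Under a constant hazard the absolute difference can still match or slightly exceed its 12-week value, because the omega-3 arm also gains events. The risk ratio and the power fall in every row.

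**The case against.** A reader might infer that the plan actually counts week 12–14 events against placebo. The documents do not support that. The quoted rule follows a sentence about reporting screening events; its evident purpose is to exclude those, not to define a complete window. A 12-week reading also has support: Description of Subjects calls the trial a 12-week double-blind investigation, the Twelve-week Study Phase text places side-effect assessment within that phase, Figure 1 labels week 12 as termination, and the follow-up visit is described as a check that mood has not worsened. Against this, Figure 1 counts 14 weeks, events are recorded throughout, and the authors wrote a week 12 limit for vital signs and laboratory values but not for adverse events. The text is ambiguous, and high confidence is justified only for the absence of a written end point.

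Exposure before week 14 is also uncertain. The protocol has patients obtain their own omega-3 after study completion. If completion means week 14, few would be taking it by the last assessment. The statement that everyone returns whatever treatment was chosen points to a start at week 12, but the two sentences do not settle it.

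A second tempting reading is that power collapses to about 20%. That needs onset clustered early: q = 30% against an assumed 40% over 12 weeks puts three quarters of the 12-week risk into the first 14 days. This is plausible for burping but is not established for adverse events in general. It also applies 50% uptake to all 30 placebo patients, whereas the protocol expects about 25% to drop out or lack usable MRS data. If all of that were dropout with no later uptake, the starters would be 0.75 × 50% = 37.5% of the arm, the placebo rate 0.10 + 0.90 × 0.375 × 0.30 = 20.1%, and the difference 19.9 points.

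Finally, this is a pilot with no power target for adverse events, and causality is assessed by the investigator and an independent physician. That helps in interpreting late events but does not change which events enter the test.

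**Conclusion.** The point holds as a gap in the analysis rule. The comparison has a start and no end, event collection runs past blinded treatment, and nothing says how events after week 12 are to be handled. Literal application would count them by randomized arm and could dilute the contrast for events caused by omega-3. Whether that happens depends on how the analyst reads the rule, whether placebo patients take omega-3 before week 14, and whether omega-3 causes the event at all.

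The size cannot be fixed from the documents. Under the assumptions above it runs from almost no change in the absolute difference (28.5–30.4 points against 30, constant hazard, half to all of the omega-3 arm continuing) to a loss of nearly half of it (16.5 points, early-clustered onset). The correction is worth making because it is cheap, and because the window should be chosen before the data are seen.

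**What to change.** In Prediction 3 and in Safety Monitoring, state that the between-arm tests of adverse and serious adverse events use events with onset from randomization to the week 12 or termination visit. This matches the window already used for vital signs and laboratory values. Randomized arm remains the basis of comparison. List events with later onset separately, by randomized arm and by whether the patient was taking omega-3 at the time. Week 14 collection and clinical follow-up stay as they are.

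The cost is a sentence or two of analysis text and two data items, onset date and omega-3 use after week 12, recorded at a visit that already takes place. The downside is that events first appearing after week 12 leave the formal test, although they are still reported.

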
Prediction 5: The relationship between changes in RBC omega-3 fatty acid levels and changes in mood symptoms is mediated by metabolite changes. This prediction is similar to Prediction 4, but more precisely specifies the mechanism by which omega-3 fatty acids are hypothesized to influence mood symptoms. Specifically, changes in RBC omega-3 fatty acid levels (which are taken to be a surrogate for omega-3 levels in the brain) are predicted to be associated with changes in metabolite levels, which will in turn influence mood symptoms. These analyses will be performed in the subsample of subjects who are randomized to treatment with omega-3 fatty acids. Prediction 5(a) is that

increases in RBC omega-3 fatty acid levels will lead to decreases in Glu and mI levels and increases in NAA levels within VLPFC and ACC. While the mediation model of Prediction 4 specifies treatment assignment as the independent variable, in this set of models we treat RBC omega-3 levels within the omega-3 treated group as the predictor variable (although all subjects will receive the same nominal treatment they will display variation in their measured omega-3 levels due to differences in metabolism, diet and treatment compliance). Prediction 5(b) is that decreases in Glu and mI levels in VLPFC and ACC, and increases in NAA in VLPFC and ACC, will lead to decreases in mood symptoms. This component is the same as Prediction 4(b), but focused on the omega-3 treated group. While the metabolite level changes were dependent variables in Prediction 5(a), in Prediction 5(b) they are independent predictors of mood symptoms. As above, the covariance of these variables will be decomposed using path analysis, with $\alpha=0.017$ used to assess significance of individual paths, and BIC used to rank competing models (e.g., simplified models with one or more paths deleted).

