- Any lifetime diagnosis of bipolar disorder not otherwise specified (NOS) or cyclothymia .

- A current diagnosis of dysthymia will not be exclusionary, if the adolescent also has a current diagnosis of MDD or Depressive Disorder NOS.
- A history of a major medical (e.g. diabetes) or neurological illness, laboratory abnormalities, or a significant episode (> 10 minutes) of loss of consciousness that could influence the MRS results, as determined by a study physician.
- Any history of alcohol or drug dependence (nicotine dependence is permitted).
- Allergy to shellfish or seafood.
- Mental retardation (IQ<70) as determined by the Wechsler Abbreviated Scale of Intelligence (WASI), administered by a research coordinator who is a trained psychometrician.
- A positive serum pregnancy test or lactating.
- A history of intolerance, hypersensitivity or non-response to omega-3 fatty acids.
- Any history of a clotting disorder that increases risk for bleeding in themselves or a first-degree relative, since omega-3 fatty acids may be associated with anti-coagulant effects.
- Concomitant use of medications with anticoagulant effects (e.g. aspirin).
- A lithium or valproate serum level of ≥ 0.4 mEq/L and 30 mg/L, respectively at baseline.
- Use of antipsychotics, other mood stabilizers, stimulants (if opting to discontinue), or atomoxetine within 72 hours (aripiprazole within two weeks will be exclusionary because of its long half-life) or antidepressants within 5 days (fluoxetine within one month will be exclusionary because of its long half-life). Patients treated with a depot antipsychotic within one dosing interval of baseline will be excluded. Subjects diagnosed with ADHD and taking a stable dose of stimulants for the previous month will be permitted to continue if it is determined necessary by subject, primary caregiver, and treating clinician report in conjunction with the study physician.
- Concomitant use of other psychotropic medications or medications with central nervous system (CNS) effects within 5 half-lives from baseline MRI scan or prior treatment with a medication with CNS effects that requires more than 5 days of a screening period.
- Any psychiatric symptom that requires admission to an inpatient psychiatric hospital, as determined by a study physician.

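### Current omega-3 supplement use is not explicitly excluded, and the available text does not restrict non-study omega-3 during the 12 weeks, so the treatment contrast can be diluted.

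*Combined protocol and SAP*

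**What the plan says.** **Eligibility (section F.3).** Besides allergy to shellfish or seafood, the only omega-3 criterion is "A history of intolerance, hypersensitivity or non-response to omega-3 fatty acids". Two nearby exclusions concern concomitant products: "Concomitant use of medications with anticoagulant effects (e.g. aspirin" and "Concomitant use of other psychotropic medications or medications with central nervous system (CNS) effects within 5 half-lives from baseline MRI scan". Both are worded for medications and neither names supplements. No criterion sets a washout for omega-3, a limit on dietary intake, or a threshold for baseline red blood cell (RBC) level.

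**Conduct (section E.a).** The paragraphs on the twelve-week phase, supplement dosing, and accountability and compliance do not address omega-3 from other sources. Compliance is judged from dispensing records.

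**Measurement (Figure 1).** "The Omega-3 Dietary Intake Questionnaire" is given at baseline, in weeks 1-11 and at week 12. "Red blood cell omega-3 fatty acid levels" are taken at screening and week 12. Both apply to all patients, and no action is attached to either.

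**Analysis (section E.b).** The Prediction 1 model names study week and treatment group as covariates and leaves other covariates and confounds to be evaluated. Prediction 5 uses RBC change as a predictor, but "These analyses will be performed in the subsample of subjects who are randomized to treatment with omega-3 fatty acids". The exploratory analyses include regressions of mood and behavior change on baseline omega-3 blood levels within each treatment group.

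**Availability (section E.a, Two-week and Long-term Follow-up).** "Omega-3 fatty acids are widely available via food, health, and supplement retail stores at a relatively low cost". This is said about use after the study.

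**The concern.** In a placebo-controlled trial of a product sold over the counter, the co-intervention that matters most is the product itself. The plan controls others closely. It sets look-back windows for antipsychotics, antidepressants and other CNS drugs, and it bars new psychotherapy and holds existing psychotherapy constant. It has no matching line for omega-3.

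Two effects follow, and they differ.

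- **Use by placebo patients during the trial** moves the placebo arm toward the active arm in mood, RBC level and metabolites. This dilutes the contrast directly.
- **Use before baseline** should be balanced between arms by randomisation, so it does not bias the comparison. It does leave users in the omega-3 arm with less room for RBC levels to rise, which weakens the contrast in change.

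With 60 patients there is little margin, and after a null result it would be hard to separate no effect from too little contrast.

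**Working it through.** **Step 1. Could another provision close the gap?**

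| Provision | What it could do | What it leaves open |
|---|---|---|
| Non-response criterion | Remove earlier users judged not to have responded | Recent starters, low-dose users, partial responders; anything after randomisation |
| Anticoagulant and CNS medication exclusions | Remove fish-oil users, if staff read them that way | Supplements are not named |
| Dispensing records and returned capsules | Track study capsules | Cannot show product bought elsewhere |
| Intake questionnaire and RBC levels | Show outside intake | No threshold, instruction or action follows |
| Exploratory regression on baseline omega-3 level | Relate starting level to outcome, in both arms | Does not use on-study intake or week-12 RBC |

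The protocol accepts that outside sources matter. Of patients in the omega-3 arm it says that "they will display variation in their measured omega-3 levels due to differences in metabolism, diet and treatment compliance". The same variation in the placebo arm has no stated use.

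**Step 2. Inputs for the size.**

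- From section F.2: 30 per arm, and effects of d = 0.6 to 0.8 regarded as clinically relevant.
- Assumed: two-sided alpha 0.05, because none is stated for Prediction 1 (0.017 is given for the path analyses and 0.05 for the exploratory ones).
- Assumed: a fraction f of placebo patients takes non-study omega-3. The documents give no rate.
- Assumed: each such patient gains a share g of the study effect.

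The available text gives no power figure for the efficacy comparison, so there is none to reproduce first.

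**Step 3. Formula.** The diluted effect is d' = d(1 - gf). Power is that of a two-sample t-test with 2 × 30 - 2 = 58 degrees of freedom and noncentrality d' × √(30/2) = 3.873 d'.

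**Step 4. Results for d = 0.8.**

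| f | d' if g = 1 | Power | d' if g = 0.5 | Power |
|---|---|---|---|---|
| 0 | 0.80 | 86% | 0.80 | 86% |
| 10% | 0.72 | 78% | 0.76 | 82.5% |
| 20% | 0.64 | 68% | 0.72 | 78% |
| 30% | 0.56 | 57% | 0.68 | not computed |

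For d = 0.6 and g = 1, power is 63% at f = 0, then 54%, 45% and 36% at f = 10%, 20% and 30%.

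**Step 5. Equivalent sample size.** With full effect in users, holding power constant multiplies N by 1/(1 - f)². That is 60/0.81 = 74.1 at f = 10% and 60/0.64 = 93.75 at f = 20%.

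**The case against.** **Other criteria may already apply.** The protocol notes that omega-3 may have anticoagulant effects, and the next exclusion concerns anticoagulant medications. Elsewhere it calls the study product a medication. A coordinator could apply that exclusion, or the CNS one, to fish oil. An established user who is still depressed enough to qualify might also count as a non-responder. This stands in part: a reader might infer that nothing keeps users out, and that goes too far. But these readings are optional, and the non-response criterion does nothing after randomisation.

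**Some text could not be checked.** The consent and assent forms (section J) and some text ahead of section E were not available. An instruction to avoid other omega-3 could be there. This limits the claim about conduct during the trial. It does not touch the eligibility list, which is complete.

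**Omega-3 levels are measured and used.** A reader might infer that no analysis uses them. The exploratory regressions on baseline levels in each arm show otherwise, and the measurements in both arms would let contamination be seen afterwards. Still, detecting it does not prevent it, and adjusting for intake after randomisation would not restore the randomised contrast.

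**The figures are an upper bound.** Full benefit in every user is unlikely. The dosing section itself reports that 200-482 mg/day was too little to reach the target RBC level and that lower EPA/DHA ratios were less effective. This stands, which is why the half-effect column is shown.

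**This is a pilot.** Aim 1 is to collect pilot data, so loss of power matters less than in a confirmatory trial. This also stands, and it bears on priority.

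**Conclusion.** The concern holds in a limited form. Current or recent omega-3 supplement use is not explicitly excluded, and the available text does not restrict it during the 12 weeks, so the contrast can be diluted. No stated rule uses on-study intake or week-12 RBC levels to identify contamination in the placebo arm.

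The size rests on an assumed rate, an assumed alpha and a simple t-test. At d = 0.8 the loss is about 8 points of power at 10% outside use and 18 points at 20% with full effect in users, or roughly 4 and 8 points with half the effect.

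Three stronger readings are not supported:

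- That the contrast *is* diluted, or that the trial will miss a real effect. No rate of outside use is given, and the remark on easy availability concerns the period after the study.
- That the arms are biased by use before baseline. Randomisation balances it in expectation.
- That the loss for mood should be computed with 22.5 per arm (30 × 0.75). The 25% in section F.2 includes unusable MRS data, while the mood model uses incomplete data.

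I would class this as a cheap improvement.

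**What to change.** 1. In section F.3, add a line on current omega-3 supplement use, with a look-back period set by the sponsor.
2. In section E.a, add an instruction not to take non-study omega-3 supplements during the 12 weeks, checked at visits with the intake questionnaire already scheduled. If the consent forms already say this, bring the wording into the protocol.
3. In Prediction 1, name baseline RBC EPA+DHA (the screening sample in Figure 1) as a prespecified covariate.
4. Report week-12 RBC EPA+DHA in the placebo arm as a descriptive contamination check, and keep the randomised comparison primary.

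The cost is protocol wording, with no new assessment. The downside is that a few current users become ineligible or must wait. Ordinary diet cannot be fully controlled, so the restriction should be limited to supplements.
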